Pharmacological and Non-pharmacological Interventions in Management of Peripheral Venipuncture related Pain: A Randomized Clinical Trial

NCT04275336

DATA: August 4,2020

STUDY PROTOCOL

Aim

This study aims to examine the effectiveness of three different interventions including EMLA cream, distraction techniques and the integrating of EMLA cream and distraction techniques in managing venipuncture pain and stress of children.

Design

A three-arm parallel, randomized controlled trial will be applied in this research. Eligible participants will be randomly assigned to into three groups: EMLA group, distraction group and combined group.

Interventions

Hard copies of informed consent will give to all parents, while children's assent and eligibility data will be obtained from face-to-face interviews. Eligible children will be randomly assigned to into three groups: EMLA group, distraction group and combined group. Nurses will explain the pain rating scales, pharmacological and non-pharmacological techniques, and the usage of intravenous cannulation. Every child will be accompanied by a parent throughout the whole process. At baseline, patients' age, sex and ethnicity will be recorded before they are grouped.

The nurse who will perform venipuncture for children had 10 years of venipuncture experience in the pediatric ward. The intravenous cannula used is 19 gauge x 0.7-in. needle and the whole procedure adhere to standard IV cannulation procedures. While cannulation is ongoing, an

observer monitor the children and complete the revised-FLACC scale (r-FLACC). The observer, a senior pediatric nurse from the surgical department who had received pain assessment training, watch the procedure through real-time surveillance video. The HR and SpO₂ of children will also be recorded.

Transparent waterproof adhesive skin dressing will use to fix the cannulation. The children and parents will give their own Wong Baker and r-FLACC ratings as soon as the procedure is over. The sample of saliva will be take using the cortisol saliva ELISA assay kit for quantitative determination of salivary cortisol levels to evaluate children's stress during venipuncture. Any adverse effects resulted from the IV cannulation or EMLA cream will be observed and recorded during their entire hospitalization.

For the EMLA group , the specialist nurse who perform IV cannulation will determine the puncture site. A thick layer of EMLA cream (lidocaine and propiocaine 2.5%/2.5%) will be applied on a 1x1 cm² area of skin on the cannulation site. The transparent dressing will be covered on the cannulation site for 30 minutes, then remove it and clean the skin with a sterile cotton swab. Then nurse will perform IV cannulation for them.

For the distraction group , multiple distractions including toy whistles, cartoon books, TV showing cartoons, and various electronic products with video games will be provided for children to choose. They will be also taught breathing exercises (i.e. inhaling through the nose for 3 seconds and exhaling for 5 seconds, while they are counting) if they are willing. A play therapist play with the children for 5 minutes prior to and throughout the venipuncture procedure.

For the combined group , both EMLA cream and distraction techniques will be used. EMLA cream will be applied on the pre-puncture site for 30 minutes as the EMLA group, then the play therapist will encourage children to choose their favorite toys and play that with them 5 minutes before venipuncture or to do breathing exercises as the distraction group. During IV cannulation the play therapist will continue distracting the child with toys.

STATISTICAL ANALYSIS PLAN

Statistical Package for Social Sciences (SPSS Inc., Chicago, IL, USA) for Windows (version 22.0) with statistical significance set to $p < 0.05$.

To answer the question that is there significant statistical difference in venipuncture pain score among lidocaine group, Attention diversion group and Combination group, Mann Whitney and Kruskal-Wallis will be used to compare the 2 and 3 groups respectively. The results will be present in a table in the form of median and interquartile range if the data is non-abnormal distribution. Otherwise, use mean±standard deviation to describe the data.

To answer the question that is there significant statistical difference in children's salivary cortisol among lidocaine group, Attention diversion group and Combination group. Mann Whitney and Kruskal-Wallis will be used to compare the 2 and 3 groups respectively. The results will be present in a table in the form of median and interquartile range if the data is non-abnormal distribution. Otherwise, use mean±standard deviation to describe the data.

To answer the question that is there significant statistical difference in children's HR, SpO₂ and venipuncture related findings like venipuncture times, venipuncture duration and indwelling needle duration of every child, Mann Whitney and Kruskal-Wallis will be used to compare the 2 and 3 groups respectively. The results will be present in a table in the form of median and interquartile range if the data is non-abnormal distribution. Otherwise, use mean±standard deviation to describe the data.

To answer the question that what's the preference for toys of children in Attention diversion group and Combination group, frequency distribution percentage will be used. To answer the question that is there significant statistical difference of children's choice in toys between Attention diversion group and Combination group, the chi-square test will be used. All the data will be present in a table in the form of median and interquartile range if the data is non-abnormal distribution. Otherwise, use mean±standard deviation to describe the data.

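### Age is recorded before allocation but used in no comparison; adjusting the pain scores for it would gain power if age has a roughly monotone relation to pain

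*Combined protocol and SAP*

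**What the plan says.** Under Interventions, the protocol says that patients' "age, sex and ethnicity will be recorded before they are grouped". On allocation it says "Eligible children will be randomly assigned to into three groups: EMLA group, distraction group and combined group"; no stratification, by age or otherwise, is described.

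The Statistical Analysis Plan sets the significance level ("with statistical significance set to $p < 0.05") and then takes the outcomes in turn:

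- **Pain score:** "Attention diversion group and Combination group, Mann Whitney and Kruskal-Wallis will be used to compare the 2 and 3 groups respectively".
- **Salivary cortisol:** the question is put as "is there significant statistical difference in children's salivary cortisol among lidocaine group, Attention diversion group and Combination group", and the same two tests are named for it.
- **HR, SpO₂ and procedure findings:** the list ends with "venipuncture times, venipuncture duration and indwelling needle duration of every child, Mann Whitney and Kruskal-Wallis will be used".

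The clause on mean and standard deviation governs only how data are described; it adds no model. Toy choice is compared by chi-square and lies outside this point. The documents mention no covariate, regression, ANCOVA, stratified test or age subgroup.

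**The concern.** Neither named test can take a covariate. A variable measured before allocation is a legitimate one, and this variable is already collected. If pain scores rise or fall with age, that variation stays in the noise against which the arms are compared, and the tests have less power than the data could give. Only power is at stake: how often a real difference between arms would be detected.

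**Working it through.** **Inputs from the documents.** Significance level 0.05 (sidedness not stated; two-sided assumed), three parallel arms, unadjusted rank tests, age recorded before allocation. The documents give no sample size, power, effect size, age range or age-outcome association, so there is no planned figure to reproduce. Every size below rests on assumed inputs.

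**Hand approximation.** Let R² be the share of outcome variance explained by age. Adjustment multiplies the residual SD by √(1 − R²). If unadjusted power is 80%, the standardised effect is 1.960 + 0.842 = 2.802, and adjusted power is Φ(2.802/√(1 − R²) − 1.960):

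- R² = 0.05: 2.802/0.975 = 2.874, power 82.0%
- R² = 0.10: 2.802/0.949 = 2.953, power 84.0%
- R² = 0.20: 2.802/0.894 = 3.132, power 87.9%
- R² = 0.30: 2.802/0.837 = 3.349, power 91.8%

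This treats the outcome as normal and the adjustment as free, so it slightly overstates the gain for a coarse score analysed by ranks.

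**Simulation.** 20,000 runs per cell, two-sided 0.05. Latent outcome = √R² × age + √(1 − R²) × normal error, with age uniform and standardised, cut into six levels at the normal sextiles. The shift between arms was set to give about 80% unadjusted power at R² = 0 and then held fixed. Mann-Whitney and Kruskal-Wallis are asymptotic and tie-corrected. Rank ANCOVA is the F test for arm with ranked age as the only covariate. Entries are power, unadjusted → adjusted.

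| Setting | R² 0.05 | R² 0.10 | R² 0.20 | R² 0.30 |
|---|---|---|---|---|
| Six levels, two arms, 50 per arm | 0.798 → 0.814 | 0.800 → 0.833 | 0.794 → 0.868 | 0.792 → 0.906 |
| Six levels, three arms, 50 per arm, one arm shifted | 0.802 → 0.817 | 0.800 → 0.839 | 0.792 → 0.872 | 0.788 → 0.912 |
| Six levels, two arms, 15 per arm | 0.800 → 0.807 | 0.798 → 0.821 | 0.799 → 0.856 | 0.788 → 0.887 |
| Heavily tied (85/12/3%), two arms, 50 per arm | 0.796 → 0.802 | 0.794 → 0.809 | 0.801 → 0.843 | 0.796 → 0.857 |

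The first row gives gains of 1.6, 3.3, 7.4 and 11.4 points. The heavily tied outcome gains about half as much at R² 0.10 to 0.30 and less than half at 0.05. The Monte Carlo standard error of a paired difference is 0.1 to 0.3 points.

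**When age does not help.** With R² = 0 (60,000 runs), Mann-Whitney against age-only rank ANCOVA:

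- 50 per arm: 0.8004 − 0.7976, a loss of 0.3 points
- 30 per arm: 0.8034 − 0.7988, a loss of 0.5 points
- 20 per arm: 0.7902 − 0.7826, a loss of 0.8 points
- 15 per arm: 0.7969 − 0.7866, a loss of 1.0 point

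With a symmetric U-shaped age effect, the change is −0.3 to 0.0 points at 50 per arm and −0.9 to −0.3 at 15. Break-even is near R² = 0.01 at 50 per arm; at 15 per arm, R² = 0.02 still gives a loss of about 0.2 points.

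**A second, uninformative covariate.** Adding a null sex term raises the losses at 50, 30, 20 and 15 per arm to 0.7, 1.2, 1.8 and 2.5 points (for example, 0.8004 − 0.7935 at 50).

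**Type I error.** 0.046 to 0.053 unadjusted and 0.047 to 0.053 adjusted.

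**The case against.** Unadjusted rank tests in a randomised trial are a legitimate choice, and preferring adjustment comes close to reviewer taste. The documents do not show that age is prognostic for anything. They list age, sex and ethnicity together, and the lack of support that would argue against using sex and ethnicity applies equally to age. The larger gains need R² of 0.20 to 0.30, which nothing in the documents supports. Nor is there any stated reason why age should predict SpO₂, the number of attempts or the indwelling time. Reporting adjusted and unadjusted tests side by side without saying which governs would create a choice of p-value that the present plan does not have.

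Most of this stands, and it limits the point. Age's prognostic value has to be written down as an assumption. Adjustment should not be imposed on every outcome. One governing test must be named for each outcome. What remains is the asymmetry: a loss of about 1 point or less in these runs if the assumption is wrong, against several points if it is right and the association is moderate.

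A reader might infer more: that the unadjusted comparisons are biased, or that the trial is underpowered because age is ignored. Neither follows. Random allocation keeps the unadjusted tests valid, and with no sample size or age association given, the power forgone may be nil.

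**Conclusion.** The point holds as an optional improvement in efficiency. It is certain from the text that age is recorded before allocation and enters no comparison. It is an assumption that age has a roughly monotone relation to pain; without that there is nothing to gain. For a six-level score with about 80% unadjusted power and 50 per arm, the gain is about 1.5, 3, 7 and 11 points at R² 0.05, 0.10, 0.20 and 0.30. It is smaller for a heavily tied outcome and somewhat smaller at 15 per arm. The documents do not show which arm size or R² applies.

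**What to change.** Before data are seen, amend the SAP as follows.

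- **Pain scores.** For each one (every rater and scale: Wong-Baker and r-FLACC from child and parent, r-FLACC from the observer), make rank ANCOVA the comparison to be interpreted. Rank the outcome and age across the children compared, then fit a linear model with arm and ranked age. Use all three arms for the overall comparison, and re-rank and refit within the two arms concerned for each pairwise one. Report the planned Kruskal-Wallis and Mann-Whitney tests alongside, labelled as unadjusted.
- **Other rank-tested outcomes.** State for each which single test governs: the age-adjusted one where age is expected to matter, otherwise the planned unadjusted test.
- **Covariates.** Use age only. Record as an assumption that age is the likeliest of the three recorded variables to be prognostic, and that each uninformative covariate costs some power.

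The cost is a few lines of SAP text and slightly more analysis; no new data are needed. The statistical cost is the small loss shown above if age is not prognostic or its effect is U-shaped. Rank ANCOVA gives no arm difference in score units, but neither do the planned tests.

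### No rating of existing pain and no record of earlier cannulation is described before allocation, and the pain tests use no covariate, not even age, so the pain comparison may give up precision that would be cheap to keep.

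*Combined protocol and SAP*

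**What the plan says.** **Before allocation.** The Interventions section lists the baseline data in one sentence: patients' "age, sex and ethnicity will be recorded before they are grouped". It also says that "children's assent and eligibility data will be obtained from face-to-face interviews", but lists neither the content of that interview nor the eligibility criteria. The section adds that "Nurses will explain the pain rating scales, pharmacological and non-pharmacological techniques". That sentence follows the one on random assignment, and the text does not state whether the explanation comes before or after allocation.

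**Pain ratings.** A trained observer completes the r-FLACC over live video during cannulation. Then: "The children and parents will give their own Wong Baker and r-FLACC ratings as soon as the procedure is over". No rating by any of the three raters is described at an earlier time.

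**Analysis.** For the pain question, which stands first in the SAP, "Mann Whitney and Kruskal-Wallis will be used to compare the 2 and 3 groups respectively". No covariate or stratification factor is named there, and no stratified randomisation is described in the protocol. The documents name no primary outcome and give no sample size, power, effect size or standard deviation.

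**The concern.** The trial takes place on a paediatric ward. Children may differ in the pain they already have, in earlier experience of cannulation and in age, and any of these may influence how pain is rated at the needle. Variation from these sources stays in the error term of an unadjusted test. A covariate measured before allocation and used in the analysis removes part of it without recruiting anyone.

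Two things stand in the way. The plan describes no measurement of current pain or earlier cannulation before allocation, and neither can be rated afresh once the cannula is in. In addition, the planned tests could not use such data if they were collected, just as they do not use age. With no sample size or power stated, nothing shows that the trial has precision to spare.

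**Working it through.** The documents contain no power or precision figure to reproduce. The calculation therefore shows what adjustment would be worth over a range of assumed correlations.

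**Inputs**
- Significance level 0.05 (SAP), taken as two-sided because sidedness is not stated.
- Assumed: 80% power for an unadjusted two-arm contrast, so the effect divided by its standard error is 1.960 + 0.842 = 2.802.
- Assumed: r, the within-arm correlation of the covariates taken together with the outcome, from 0.2 to 0.5.

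**Formulas**
- Residual variance ratio: 1 − r².
- Equivalent increase in sample size: 1/(1 − r²) − 1.
- Power after adjustment: Φ(2.802/√(1 − r²) − 1.960).
- Children per arm for an assumed effect of 0.5 SD, 80% power, equal arms: 2 × 2.802²/0.5² × (1 − r²) = 62.8 × (1 − r²), rounded up.

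| r (assumed) | Variance removed | Equivalent extra children | Power, from 80% | Children per arm, from 63 |
|---|---|---|---|---|
| 0.2 | 4% | 4.2% | 81.6% | 61 |
| 0.3 | 9% | 9.9% | 83.6% | 58 |
| 0.4 | 16% | 19.0% | 86.4% | 53 |
| 0.5 | 25% | 33.3% | 89.9% | 48 |

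For r = 0.4: 1 − 0.16 = 0.84; 1/0.84 − 1 = 0.190; √0.84 = 0.917; 2.802/0.917 − 1.960 = 1.097; Φ(1.097) = 0.864.

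**Does the gain survive rank methods?** These formulas are for means. A simulation with 2,000 runs per setting used three arms of an assumed 40 children, a rounded 0–10 score and one arm shifted by 0.5 SD. It compared Kruskal-Wallis with a rank analysis of covariance that fits arm and covariate together on ranks. This is a close relative of Quade's two-step method, not the same calculation.

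| r | Power, Kruskal-Wallis | Power, rank ANCOVA |
|---|---|---|
| 0 | 0.59 | 0.59 |
| 0.3 | 0.59 | 0.63 |
| 0.5 | 0.57 | 0.72 |

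With no true difference, rejection rates for both methods lay between about 0.049 and 0.054. The unadjusted tests are therefore valid, and the adjusted one gains power in step with r.

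**What the new items add beyond age.** Age is already recorded, so part of the gain needs no new data. As an illustration, suppose age alone gave r = 0.3. Raising the joint correlation to 0.4 would then cut the remaining variance by (0.91 − 0.84)/0.91 = 7.7%, and raising it to 0.5 by (0.91 − 0.75)/0.91 = 17.6%. The documents do not allow this split to be estimated.

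**The case against.** The strongest reply is that this is an optional gain of unknown size. Randomisation balances existing pain and earlier experience on average, the rank tests hold their type I error, and nothing in the documents places r above 0.2, where the gain is about 4%. All of this stands. It limits the importance of the point but does not remove it, because the cost of the change is also small.

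A second reply is that the eligibility interview might already cover current pain or earlier cannulation. That is possible, since its content is not listed. The accurate statement is that no such item is described, and the planned tests would not use it in any case.

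Four stronger readings are tempting, and the documents do not support them.
- *The comparison is biased, or a chance imbalance would invalidate it.* Such imbalance is already allowed for in the type I error of the tests.
- *Pain rests on one score taken after the procedure.* The observer r-FLACC is completed during cannulation, and child and parent each rate afterwards.
- *A baseline would let the trial separate needle pain from pain already present.* Adjustment sharpens the comparison between arms; it does not divide a child's score by source.
- *Asking how much the needle is expected to hurt would be harmless if done before allocation.* The EMLA and combined arms have a stated 30-minute wait under the cream, while the distraction arm has only 5 minutes of play stated. The time from question to needle could differ by arm, and any priming effect with it.

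**Conclusion.** The point holds as one of precision. The described baseline set omits existing pain and earlier cannulation, and the pain analysis uses no covariate, including the age that is recorded. The loss is r² of the outcome variance: 4% to 25% for assumed joint correlations of 0.2 to 0.5, or power of about 82% to 90% where the unadjusted test would have 80%. Both the correlation and the 80% starting point are assumptions. The gain is slight at r of about 0.2 or less and material from about 0.4. Validity is not in question, so this is an inexpensive improvement to the plan and not the correction of an error.

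**What to change.** **Protocol, Interventions.** State that the Wong-Baker scale is explained before allocation. Then, still before allocation, take one Wong-Baker rating of current pain from the child and record whether the child has been cannulated before. Leave out a question on expected pain, or make it optional, because of possible priming.

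**SAP, pain question.** Prespecify rank analysis of covariance (Quade) for the pain scores, for both the three-group and the pairwise comparisons, with age, baseline pain and earlier cannulation as covariates. In SPSS this can be built from three steps: rank the outcome and covariates, regress the outcome ranks on the covariate ranks, and compare the residuals between arms. Keep the Mann-Whitney and Kruskal-Wallis tests as supporting analyses. Do not describe the adjusted result as isolating needle pain.

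**Cost.** A short addition to an interview already planned, possibly an earlier explanation of the scale, two data fields and one more analysis. Baseline pain has to be collected before the needle, so that part must be settled before a child is enrolled. Adjustment for age needs no new data and could be prespecified on its own. The return may be small if the covariates turn out to be weakly related to the ratings.

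### HR and SpO₂ are compared between arms with no reading before allocation and no adjustment, which gives up precision that one resting reading could recover

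*Combined protocol and SAP*

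**What the plan says.** The Interventions section of the protocol lists what is collected before allocation: "At baseline, patients' age, sex and ethnicity will be recorded before they are grouped". HR and SpO₂ are not in that list. They appear once in the protocol, in the paragraph on observation during cannulation: "The HR and SpO₂ of children will also be recorded". No time point, number of readings or summary (peak, mean, last) is given.

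The Statistical Analysis Plan asks "is there significant statistical difference in children's HR, SpO₂ and venipuncture related findings" and answers that "Mann Whitney and Kruskal-Wallis will be used to compare the 2 and 3 groups respectively". It names no baseline value, change score or covariate for these measures.

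Allocation is random: "Eligible participants will be randomly assigned to into three groups: EMLA group, distraction group and combined group".

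**The concern.** HR bears on the aim of managing pain and stress mainly as a reaction to the procedure. Children differ in resting HR for reasons unrelated to the intervention. Without a resting reading, that spread stays in the error term of the between-arm comparison. An invented example shows the limit: a child who goes from 80 to 110 beats per minute and a child who stays at 110 give the same value.

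The trial compares three active approaches and has no untreated arm. If the true HR differences between arms are modest, lost precision makes them easier to miss. A chance imbalance in resting HR could not be seen or corrected.

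The reading has to come before grouping. Afterwards the waiting period differs by arm: two arms have cream under a dressing for 30 minutes, and two have 5 minutes of play or breathing exercises. A reading taken just before the needle could already reflect the allocated intervention.

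**Working it through.** The documents give no sample size, effect size, standard deviation or baseline-to-procedure correlation, so there is no planned figure to reproduce. The check shows what adjustment would be worth over a range of assumed correlations.

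**Inputs from the documents:** three randomised arms; significance at 0.05; unadjusted Kruskal-Wallis and Mann-Whitney tests on levels.

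**Assumptions:** two-sided test; equal arms; equal standard deviations at rest and at the procedure; a standardised difference of 0.5; 80% power for a comparison of two arms; r as listed.

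**Step 1, unadjusted levels.** n per arm = 2 × (1.960 + 0.842)² / 0.5² = 2 × 7.85 / 0.25 = 62.8, so 63.

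**Step 2, baseline adjustment.** Variance relative to unadjusted levels = 1 − r². Efficiency = 1/(1 − r²).

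**Step 3, plain change score.** Variance relative to unadjusted levels = 2(1 − r).

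| r (assumed) | 1 − r² | Efficiency | n per arm, adjusted | Power at 63 per arm, adjusted | 2(1 − r) | n per arm, change score |
|---|---|---|---|---|---|---|
| 0.3 | 0.91 | 1.10 | 58 | 83.7% | 1.4 | 88 |
| 0.5 | 0.75 | 1.33 | 48 | 90.0% | 1.0 | 63 |
| 0.7 | 0.51 | 1.96 | 33 | 97.6% | 0.6 | 38 |

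Adjustment helps at every r shown. The change score gains nothing at r = 0.5 and needs more children below that (88 against 63 per arm at r = 0.3).

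**Step 4, the planned type of test.** Kruskal-Wallis was simulated on unadjusted levels and on residuals from a linear regression on baseline. The settings were normal data, three arms of 64, one arm shifted by 0.5 standard deviations, and 3,000 runs per setting.

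| r (assumed) | Power, unadjusted | Power, adjusted |
|---|---|---|
| 0.3 | 80.9% | 84.4% |
| 0.5 | 81.8% | 90.5% |
| 0.7 | 80.3% | 97.9% |

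With no true difference, the unadjusted test rejected in 4.1% to 5.5% of runs for r from 0 to 0.8. It keeps its level, so the missing baseline costs precision and does not create false positives.

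**Step 5, how much of the gain age already supplies.** Age is recorded, so it could be adjusted for without new data. Suppose age correlates at −0.5 with both the resting and the procedural reading (assumption). The partial correlation is then (r − 0.25)/(1 − 0.25):

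- r = 0.3: 0.05/0.75 = 0.07, further efficiency 1.00
- r = 0.5: 0.25/0.75 = 0.33, further efficiency 1.13
- r = 0.7: 0.45/0.75 = 0.60, further efficiency 1.56

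Under this assumption, the gain from the new reading beyond age runs from almost nothing to about half as many children again.

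**The case against.** The strongest reply is that this is an optional gain on supporting measures, not a validity defect. Four readings that go further than the documents allow should be set aside.

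- A reader might infer that the HR comparison is biased, or that a finding of no difference would be uninterpretable. Neither follows. Under random allocation, resting level balances in expectation and the arm difference in procedural level estimates the intervention effect. The 80-to-110 example concerns individual children, not the difference between arms. A non-significant result can be read through its confidence interval, as for any unadjusted outcome.
- A reader might infer that the levels mostly rank children by resting HR. At r from 0.5 to 0.7, resting HR explains 25% to 49% of the variance, which is less than half.
- A reader might infer that a single reading is taken. The text leaves the number and timing open. That is a gap of its own, and the fix has to close it.
- A reader might treat HR as the measure that carries the stress objective. The protocol gives that role to salivary cortisol. The SAP takes HR and SpO₂ after pain and cortisol, grouped with number of attempts and durations.

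It is also fair that the size rests on an assumed r, that it is modest at 0.3, and that part of it overlaps with age. No figure for SpO₂ can be derived.

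These replies limit the point but do not remove it. No reading before allocation is planned, the SAP does not adjust, and the information cannot be recovered once the child has been allocated and the intervention has begun.

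**Conclusion.** The gap is real and its consequence is limited. The planned comparison of HR and SpO₂ is unbiased, but it is less precise than it could be, is open to chance imbalance in resting level, and cannot describe each child's change from rest.

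For assumed r of 0.3, 0.5 and 0.7, baseline adjustment is worth 1.10, 1.33 and 1.96 times as many children for this comparison. The gain beyond age adjustment is smaller. For SpO₂ it is probably smaller too, because values are likely to cluster near the top of the scale. These figures rest on normal-theory variance formulas with equal standard deviations and on correlations that the documents do not supply.

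Because these measures are listed after pain and cortisol, the main conclusion does not turn on this point. The change is still worth making, because it costs little and improves on the unadjusted test as written.

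**What to change.** 1. At the existing baseline step, before grouping, take one resting HR and SpO₂ reading with the monitor that will be used at the procedure.
2. Define the procedural reading by the same event in all arms (first needle insertion, for example), and state how many readings are taken and how they are summarised.
3. In the SAP, compare arms with adjustment for the baseline reading and age, for example by rank-based ANCOVA. Keep the unadjusted Kruskal-Wallis and Mann-Whitney tests as supporting.
4. Show change from baseline descriptively only, because an unadjusted change score loses precision when r is below 0.5.
5. State a simple rule for a missing baseline value that ignores arm, such as filling in the median over all children.

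The cost is one short non-invasive reading with equipment already in use, one form field, a few lines in the SAP and the missing-value rule. No extra staff are needed. For children already allocated, the resting reading cannot be recovered. Adjustment for age alone is still possible for them, and the report should state the limitation.

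### Salivary cortisol is compared between arms without using the clock time of the sample, which leaves the hormone's daily fall in the comparison, mainly as avoidable noise

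*Combined protocol and SAP*

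**What the plan says.** The protocol's Aim names children's stress alongside pain. Under Interventions, after the cannula is fixed and the pain ratings are given, "The sample of saliva will be take using the cortisol saliva ELISA assay kit for quantitative determination of salivary cortisol levels", and the stated purpose is "to evaluate children's stress during venipuncture". No hour, sampling window or pre-procedure sample is described. The baseline data are limited: "At baseline, patients' age, sex and ethnicity will be recorded before they are grouped".

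The Statistical Analysis Plan poses the question of a difference in "salivary cortisol among lidocaine group, Attention diversion group and Combination group" and answers it as follows: "Mann Whitney and Kruskal-Wallis will be used to compare the 2 and 3 groups respectively". It names no covariate or stratum. Allocation is random, with no mention of blocking or stratification by time.

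Preparation before the needle differs by arm. In the EMLA group, "The transparent dressing will be covered on the cannulation site for 30 minutes". The distraction group has 5 minutes of play first. The combined group has the 30 minutes of cream and then the 5 minutes of play, about 35 minutes in all.

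**The concern.** Cortisol is high in the morning and falls through the day. Two equally stressed children sampled at 09:00 and 16:00 would be expected to give different values. This is separate from the interval between needle and sample: fixing that interval exactly would leave the effect of the hour untouched.

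Three features of the plan let this variation through. The sample's hour is neither restricted nor stated to be recorded. No pre-procedure value is described, so no change score or baseline adjustment can offset it. The rank tests take no covariate. What is at stake is precision on the plan's biochemical measure of stress. In addition, unless sampling times are kept, nobody could check afterwards whether the arms were sampled at similar hours.

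**Working it through.** The plan states no sample size, power, SD or target difference for cortisol, so it has no figure to reproduce. What follows is illustrative.

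**Inputs**
- From the protocol's Interventions section: preparation of 30, 5 and about 35 minutes. The gaps against distraction are 30 − 5 = 25 and 35 − 5 = 30 minutes.
- Assumed: cortisol falls by a factor f = 2 to 4 over a 9-hour working day, linearly on the log scale; the between-child SD of log cortisol at a fixed hour is w = 0.5 to 0.7; samples are spread evenly over a window of W = 2, 4 or 9 hours.

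**Noise**

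Slope b = ln(f)/9, which is 0.0770 per hour for f = 2 and 0.1540 for f = 4.
Variance due to clock time v = b²W²/12.
Share of variance R² = v/(v + w²).
Value of full adjustment, as a multiple of the number of children, 1/(1 − R²) = 1 + v/w².

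| Window W | f | v | R² (w = 0.7) | R² (w = 0.5) | Multiple (w = 0.7 to 0.5) |
|---|---|---|---|---|---|
| 2 h | 2 | 0.0020 | 0.4% | 0.8% | 1.004 to 1.008 |
| 2 h | 4 | 0.0079 | 1.6% | 3.1% | 1.016 to 1.032 |
| 4 h | 2 | 0.0079 | 1.6% | 3.1% | 1.016 to 1.032 |
| 4 h | 4 | 0.0316 | 6.1% | 11.2% | 1.065 to 1.127 |
| 9 h | 2 | 0.0400 | 7.6% | 13.8% | 1.08 to 1.16 |
| 9 h | 4 | 0.1602 | 24.6% | 39.0% | 1.33 to 1.64 |

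The window, on which the documents are silent, matters as much as the steepness of the fall.

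A second set of assumptions gives the same picture. With b = 0.05 to 0.15 per hour, w = 0.4 to 0.8 and W = 2 to 8 hours, the required number rises by 0.1% to 75%. For a 0.5 SD effect at 80% power and two-sided 0.05, 63 per arm with clock time removed becomes 66 at b = 0.10, w = 0.6 and W = 4 hours, 73 at W = 8 hours, and 110 in the most extreme corner.

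**Shift from preparation time alone**

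Suppose preparation starts at similar hours in all arms. Cream-arm samples then fall 25 or 30 minutes later than distraction samples. The log shift is b × gap:
- f = 2: 0.032 to 0.039, that is 3.2% to 3.8% lower in the cream arms.
- f = 4: 0.064 to 0.077, that is 6.2% to 7.4% lower.

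Divided by the total SD √(v + w²), this is 0.04 to 0.15 SD over all the windows above. As a reference point, a shift of 0.083 SD would raise the false-positive rate of one pairwise test, normal approximation, from 5% to 6.2% with 30 per arm, 7.4% with 60 and 9.0% with 100. These arm sizes are assumed.

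**The case against.** The strongest reply is that this concerns efficiency, not validity. Children are randomised, so the hour of sampling is balanced on average and the unadjusted rank tests stay close to their nominal error rate. With no sample size, SD or target difference in the plan, nobody can show that the noise would hide a real effect. That stands, and the point is framed accordingly.

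The spread of sampling hours is also unknown. If study cannulations already cluster within 2 hours, adjustment gains at most about 3%. That stands too, and is why the range starts near zero.

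A reader might infer that clock time goes wholly unlogged. The documents do not support this. The Statistical Analysis Plan analyses how long the cannula stays in, which normally needs a logged insertion time, so an approximate hour may be recoverable. The same list includes venipuncture times, which most naturally means the number of punctures; even as clock time it would be an outcome there, not an adjuster for cortisol. What can be said is that the plan does not state that the sample's time is recorded and does not use it.

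A reader might also infer that the ward fits the short and long preparations into different parts of the shift, so that the daily rhythm appears as a treatment effect. Nothing in the documents says so. The only arm-linked timing they contain is the 25 to 30 minute preparation gap.

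**Conclusion.** The point holds as an avoidable loss of precision. Clock time is neither stated to be recorded for the saliva sample nor used in the cortisol comparison, and there is no baseline cortisol to offset it. Adjustment is worth between almost nothing (2-hour window) and 1.64 times as many children (9-hour window, four-fold fall, SD 0.5). The upper end is a corner of the assumptions, not an expectation. The preparation gap could add a systematic shift of about 3% to 7%, which is small but does not shrink with sample size; it assumes that preparation starts at similar hours in each arm.

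The size of the daily fall, the between-child SD and the sampling window are all assumptions. The documents do not support reading this as a material bias, or as an error that invalidates the planned test.

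**What to change.** Add a field for the clock time of each saliva sample. In the salivary cortisol paragraph of the Statistical Analysis Plan, specify log cortisol modelled on arm and clock time or, to stay with ranks, a rank test stratified by time-of-day band. Report the distribution of clock time by arm. The model also addresses the preparation-gap shift; broad bands would remove the noise but only part of a half-hour difference.

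The cost is one form field and a slightly more complex analysis. No extra sample or staff is needed, and the timing of cannulation does not have to change. The field should be in place before collection starts, because an exact sampling time may not be recoverable later.
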